2. TYPE OF PLANNED ANALYSIS

2.1. Interim Analyses

No formal interim analyses are planned.

2.2. Final Analysis

After all subjects have completed the study, outstanding data queries have been resolved or adjudicated as unresolvable, and the data have been cleaned and finalized, the final analysis of the data will be performed.

3. GENERAL CONSIDERATIONS FOR DATA ANALYSES

Analysis results will be presented using descriptive statistics. For categorical variables, the number and percentage of subjects in each category will be presented; for continuous variables, the number of subjects (n), mean, standard deviation (StD) or standard error (SE), median, first quartile (Q1), third quartile (Q3), minimum, and maximum will be presented.

By-subject listings will be presented for all subjects in the All Enrolled Analysis Set and sorted by subject ID number, visit date, and time (if applicable). Data collected on log forms, such as AEs, will be presented in chronological order within the subject. The treatment group to which subjects were initially assigned will be used in the listings. Age, sex at birth, race, and ethnicity will be included in the listings, as space permits.

3.1. Analysis Sets

Analysis sets define the subjects to be included in an analysis. Analysis sets and their definitions are provided in this section. The analysis set will be identified and included as a subtitle of each table, figure, and listing.

For each analysis set, the number and percentage of subjects eligible for inclusion will be summarized by treatment group.

A listing of reasons for exclusion from analysis sets will be provided by subject.

3.1.1. All Enrolled Analysis Set

All Enrolled Analysis Set includes all subjects who received a study subject identification number in the study after screening.

3.1.2. Full Analysis Set

The Full Analysis Set (FAS) includes all subjects who took at least 1 dose of study drug with treatment group designated according to the planned treatment. This is the primary analysis set for efficacy analyses. Throughout this SAP, study drug is defined as any drug in the therapy (GS-5829 or enzalutamide) unless specified otherwise.

3.1.3. Safety Analysis Set

The Safety Analysis Set includes all subjects who took at least 1 dose of study drug. This is the primary analysis set for safety analyses.

3.1.4. Dose-Limiting Toxicity (DLT) Analysis Set

The DLT Analysis Set includes all subjects in the Safety Analysis Set who complete all or at least 21-day study treatment and have safety assessment through Day 28 of GS-5829, inclusive, or experienced a DLT prior to Day 28, exclusive. During the DLT assessment window, if a subject who fails to receive GS-5829 for at least 21 days for reasons other than DLT, another

subject will be enrolled at the same dose level for replacement. For subjects who are replaced but received at least 1 dose of study drug, they will be included in the Safety Analysis Set and not in the DLT Analysis Set.

3.1.5. Pharmacokinetic Analysis Set

The Pharmacokinetic (PK) Analysis Set will include all enrolled subjects who took at least 1 dose of study drug and have at least 1 nonmissing postdose concentration value reported by the PK laboratory. This is the primary analysis set for all PK analyses.

3.2. Subject Grouping

For analyses based on the FAS, subjects will be grouped according to the treatment to which they were assigned. For analyses based on the Safety Analysis Set, subjects will be grouped according to actual treatment received. The actual treatment received will differ from the assigned treatment only when their actual treatment differs from assigned treatment for the entire treatment duration.

For the PK Analysis Set, subjects will be grouped according to the actual treatment they received.

3.3. Strata and Covariates

This study does not use a stratified randomization schedule when enrolling subjects. No covariates will be included in efficacy and safety analyses.

3.4. Examination of Subject Subgroups

There are no prespecified subject subgroupings for efficacy and safety analyses.

3.5. Multiple Comparisons

Adjustments for multiplicity will not be made, because no formal statistical testing will be performed in this study.

3.6. Missing Data and Outliers

3.6.1. Missing Data

In general, missing data will not be imputed unless methods for handling missing data are specified. Exceptions are presented in this document.

For missing last dosing date of study drug, imputation rules are described in Section 4.2.1. The handling of missing or incomplete dates for AE onset is described in Section 7.1.5.2, and for prior and concomitant medications in Section 7.4.

3.6.2. Outliers

Outliers will be identified during the data management and data analysis process, but no sensitivity analyses will be conducted. All data will be included in the data analysis.

3.7. Data Handling Conventions and Transformations

The following conventions will be used for the imputation of date of birth when it is partially missing or not collected:

- If only month and year of birth is collected, then “15” will be imputed as the day of birth
- If only year of birth is collected, then “01 July” will be imputed as the day and month of birth
- If year of birth is missing, then date of birth will not be imputed

In general, age (in years) collected on the date of the first dose of study drug will be used for analyses and presentation in listings. If age at Day 1 is not available for a subject, then age derived based on date of birth and the Day 1 visit date will be used instead. If an enrolled subject was not dosed with any study drug, the enrollment date will be used instead of the first dosing date of study drug. For screen failures, the date the first informed consent was signed will be used for age derivation. Age required for longitudinal and temporal calculations and analyses (eg, estimates of creatinine clearance, age at date of AE) will be based on age derived from date of birth and the date of the measurement or event, unless otherwise specified.

Non-PK data that are continuous in nature but are less than the lower limit of quantitation (LOQ) or above the upper LOQ will be imputed as follows:

- A value that is 1 unit less than the LOQ will be used to calculate descriptive statistics if the datum is reported in the form of “ $< x$ ” (where x is considered the LOQ). For example, if the values are reported as < 50 and < 5.0 , values of 49 and 4.9, respectively, will be used to calculate summary statistics. An exception to this rule is any value reported as < 1 or < 0.1 , etc. For values reported as < 1 or < 0.1 , a value of 0.9 or 0.09, respectively, will be used to calculate summary statistics.
- A value that is 1 unit above the LOQ will be used to calculate descriptive statistics if the datum is reported in the form of “ $> x$ ” (where x is considered the LOQ). Values with decimal points will follow the same logic as above.
- The LOQ will be used to calculate descriptive statistics if the datum is reported in the form of “ $\leq x$ ” or “ $\geq x$ ” (where x is considered the LOQ).

If methods based on the assumption that the data are normally distributed are not adequate, analyses may be performed on transformed data or nonparametric analysis methods may be used, as appropriate.

Natural logarithm transformation will be used for plasma/blood concentrations and analysis of PK parameters. Plasma concentration values that are below the limit of quantitation (BLQ) will be presented as “BLQ” in the concentration data listing. Values that are BLQ will be treated as 0 at predose time points, and one-half the value of the LOQ at postbaseline time points, where LOQ is corrected for the dilution factor (ie, reported LOQ/dilution factor) for determination of summary and order statistics.

The following conventions will be used for the presentation of summary and order statistics:

- If at least 1 subject has a concentration value of BLQ for the time point, the minimum value will be displayed as “BLQ.”
- If more than 25% of the subjects have a concentration data value of BLQ for a given time point, the minimum and Q1 values will be displayed as “BLQ.”
- If more than 50% of the subjects have a concentration data value of BLQ for a given time point, the minimum, Q1, and median values will be displayed as “BLQ.”
- If more than 75% of the subjects have a concentration data value of BLQ for a given time point, the minimum, Q1, median, and Q3 values will be displayed as “BLQ.”
- If all subjects have concentration data values of BLQ for a given time point, all order statistics (minimum, Q1, median, Q3, and maximum) will be displayed as “BLQ.”

PK parameters that are BLQ will be imputed as one-half LOQ before log transformation or statistical model fitting.

3.8. Analysis Visit Windows

3.8.1. Definition of Study Day

Study day will be calculated from the first dosing date of study drug and derived as follows:

- For postdose study days: Assessment Date – First Dosing Date + 1
- For days prior to the first dose: Assessment Date – First Dosing Date

Therefore, study day 1 is the day of first dose of study drug administration.

3.8.2. Analysis Visit Windows

The nominal visit as recorded on the CRF will be used when data are summarized by visit. Any data relating to unscheduled visits will not be assigned to a particular visit or time point.

However, the following exceptions will be made:

- An unscheduled visit prior to the first dosing of study drug may be included in the calculation of the baseline value, if applicable.
- Unscheduled visits after the first dosing of study drug will be included in determining the maximum postbaseline toxicity grade.
- For subjects who prematurely discontinue from the study, early termination (ET) data will be assigned to what would have been the next scheduled visit where the respective data were scheduled to be collected.
- Data collected on a follow-up visit will be summarized as a separate visit and labeled “Follow-up Visit.”
- Data obtained after the follow-up visit or last dose date plus 30 days (whichever is later) will be excluded from the summaries but will be included in the listings.

3.8.3. Selection of Data in the Event of Multiple Records in an Analysis Visit Window

Depending on the statistical analysis method, single values may be required for each analysis window. For example, change from baseline by visit usually requires a single value, whereas a time-to-event analysis would not require 1 value per analysis window.

If multiple, valid nonmissing measurements exist in an analysis window, records will be chosen based on the following rules if a single value is needed:

- For baseline, the last nonmissing value on or prior to the first dosing date of study drug (GS-5829 or enzalutamide) will be selected, unless specified differently. If there are multiple records with the same time or no time recorded on the same day, the baseline value will be the average of the measurements for continuous data, or the measurement with the lowest severity (eg, normal will be selected over abnormal for safety electrocardiogram [ECG] findings) for categorical data.
- For postbaseline visits:

The record closest to the nominal day for that visit will be selected.

If there are 2 records that are equidistant from the nominal day, the later record will be selected.

If there is more than 1 record on the selected day, the average will be taken for continuous data and the worse severity will be taken for categorical data, unless otherwise specified.

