### 3.3. Study Treatments

Subjects who meet eligibility criteria will receive GS-5829 as a single agent or combined with enzalutamide orally once daily. Each cycle will consist of 28 days. Safety and efficacy assessments will occur on an outpatient basis including assessment of tumor response, physical exam, vitals, electrocardiogram (ECG), collection of blood samples (for routine safety labs, GS-5829 PK, PD markers, and biomarkers at applicable visits), and assessment of AEs. In addition, subjects will undergo a bone scan and CT (or MRI) every 12 weeks.

A subject who does not show evidence of disease progression may continue receiving GS-5829 as a single agent or combined with enzalutamide once daily until disease progression (clinical or radiographic), unacceptable toxicity, withdrawal of consent, or other reasons specified in Section 3.4. Subjects who have progressive disease by PSA measurements alone may continue study drug.

Following treatment, subjects will be followed for safety for 30 days and for survival.

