#### 6.2.9.2. CT or MRI

Subjects will be assessed by CT scan with contrast (or MRI, if unable to tolerate CT contrast) of the chest, abdomen and pelvis to document metastatic disease, identify target lesions and to assess response as per PCWG2 guidelines.

In subjects who cannot tolerate iodinated contrast, a CT of the lung without contrast and MRI of the abdomen should be performed. Imaging by CT scan (with contrast) or MRI or applicable scan will be performed at Screening (within 8 weeks before Cycle 1 Day 1 if the scan was performed as part of standard medical practice) and every 12 weeks during the treatment period regardless of cycle number or dose interruption. During the treatment, scans may be performed at time points other than 12 weeks, as clinically indicated, to assess tumor progression.

Tumor burden will be characterized at baseline and subsequent response assessments will be carried out according to the PCWG2 Criteria. The same radiographic procedure and specification (eg, the same contrast agent, slice thickness, etc.) used to define measurable lesions at baseline must be used throughout the study for each subject.

Please refer to [Appendix 5](#) for additional information on PCWG2 study progression criteria.

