#### **6.5.5. End of Treatment (EOT) Visit**

The following procedures will be conducted when a subject discontinues GS-5829, with a window of  $\pm$  7 days, and prior to initiating a new anti-cancer regimen:

- Complete Physical examination, including weight
- Vital signs (pre-dose only)
- Triplicate 12-lead ECG
- ECOG performance status
- Laboratory assessments and blood sampling
  - Chemistry
  - CBC with differential
  - Coagulation
  - Urinalysis
  - PSA
- **cci** [REDACTED]
- Bone scan (not necessary if restaging scan was performed within the prior 4 weeks)
- CT with contrast or MRI (not necessary if restaging scan was performed within the prior 4 weeks)
- Record any adverse events
- Concomitant medications review
- IP/Dosing Diary accountability

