- Coagulation assessment includes PT/PTT, fibrinogen, Factor VII, fibrinogen degradation products (FDP).
- In Phase 1b dose escalation with enzalutamide: PK samples will be collected on Day 1 and Day 15 of Cycle 1 at pre-dose 0.5, 1, 2, 3, 4, 6, 8 and 24 hours post-dose and anytime on Day 1 of Cycles 2 through 6. In Phase 2 dose expansion Group 2: PK samples will be collected on Cycle 2, Day 1 at pre-dose and 1, 2, 4, and 6 hours post-dose. Sparse PK will be collected at pre-dose and 1 - 4 hours post-dose on Cycle 1 Day 1 and Day 15 and anytime on Day 1 of Cycles 3 through 6. In Phase 2 dose expansion Group 3: PK samples will be collected on Cycle 2, Day 1 at pre-dose and 1, 2, 4, and 6 hours post-dose. Sparse PK and PD samples will be collected at pre-dose and 1 - 4 hours post-dose on Cycle 1, Day 1 and Day 15 and anytime on Day 1 of Cycles 3 through 6.
- In Phase 1b dose escalation with enzalutamide: PD biomarker samples will be collected on Day 1 and Day 15 of Cycle 1 at pre-dose, 0.5, 1, 2, 3, 4, 6, 8, and 24 hours post-dose and anytime on Day 1 of Cycles 2 through 6. In Phase 2 dose expansion Group 2: PD samples will be collected on Day 15 of Cycle 1 at pre-dose and 1, 2, 4, and 6 hrs post-dose. Sparse PD will be collected at pre-dose and 1-4 hours post-dose on Cycle 1 Day 1 and Day 8 and anytime on Day 1 of Cycles 2 through 6. In Phase 2 dose expansion Group 3: PD samples will be collected on Cycle 2, Day 1 at pre-dose and 1, 2, 4, and 6 hours post-dose. Sparse PK and PD samples will be collected at pre-dose and 1 - 4 hours post-dose on Cycle 1, Day 1 and Day 15 and anytime on Day 1 of Cycles 3 through 6.

CCI

13. Tumor markers PSA will be collected on C1D1 at pre-dose and on Day 1 of every subsequent Cycle at pre-dose.
14. If available, paraffin embedded archival tumor tissue block for shipment to Gilead or its designee will be requested at C1D1.

CCI

16. Tumor evaluation by CT/MRI or applicable scan will be performed during screening (within 8 weeks of Cycle 1 Day 1) and every 12 weeks thereafter. The same radiographic procedure used to define measurable lesions must be used throughout the study for each subject. CT/MRI to be done at EOT visit if not done within the previous 4 weeks.
17. Subjects will also undergo a bone scan. Scan at EOT visit is not necessary if the previous scan is performed within 4 weeks of the EOT.

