6.2. Secondary Efficacy Endpoints

6.2.1. Definition of Secondary Efficacy Endpoints

PSA response, defined as $\geq 30\%$ decline in PSA from baseline at 12 weeks.

Overall response by lesion scan only: subjects will be categorized based on PCWG2 criteria of lesion scans (same with RECIST v. 1.1 for lesion scans) as complete response (CR), partial response (PR), stable disease (SD), non-complete response or non-progressive disease, progressive disease (PD) or not evaluable (NE) at each visit of assessment.

Overall survival (OS), defined as the interval from start of study drug to death from any cause. Subjects who are lost to follow-up or survived until the end of the study will be censored at the last date that they were known to be alive.

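### SAP 3.8.2 moves early-termination data to the next scheduled visit without exempting efficacy, so a PSA taken up to about 28 days early can be counted as the Week-12 result

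*SAP*

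**What the plan says.** SAP 3.8.2 opens with the general rule: "The nominal visit as recorded on the CRF will be used when data are summarized by visit". Among its exceptions, for subjects who leave the study prematurely, is that "early termination (ET) data will be assigned to what would have been the next scheduled visit where the respective data were scheduled" for collection. No maximum gap is set, and nothing limits the exception to safety data.

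The schedule fixes how far a value can move. "Each cycle will consist of 28 days" (Protocol 3.3), and "Tumor markers PSA will be collected on C1D1 at pre-dose and on Day 1 of every subsequent Cycle at pre-dose" (Protocol Appendix 3; Appendix 2 has the same rule for monotherapy). PSA is also taken at End of Treatment. Scans are due "every 12 weeks during the treatment period regardless of cycle number or dose interruption" (Protocol 6.2.9.2). The End of Treatment visit adds "CT with contrast or MRI (not necessary if restaging scan was performed within the prior 4 weeks") (Protocol 6.5.5). Treatment-period visits and scans carry a ±7-day window.

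The outputs in question are:
- PSA response, a 30% or greater "decline in PSA from baseline at 12 weeks" (SAP 6.2.1). SAP 6.2.2 gives no date window and no rule for subjects without a value.
- Lesion response, categorised at each assessment visit (SAP 6.2.1).
- The Week-24 non-progression rate, given as a Kaplan-Meier estimate from PFS and also by simple counting (SAP 6.1.2).

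**The concern.** Applied as written, the rule gives a value from a subject who has left the label of a visit that subject never reached. A favourable PSA at about Week 8 can become a Week-12 response. An unfavourable one can become a Week-12 non-response on the strength of a rise before 12 weeks, which Appendix 5 says to disregard when judging PSA response. A non-progressing scan from about Week 16 can stand in for Week 24.

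SAP 3.8.3 prefers the record closest to the nominal day, but only where several records compete. It does nothing when the relabelled record is the only one. The dose-level groups are small, so a single reassigned subject visibly changes a reported rate, and the reader of the table cannot see that it happened.

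**Working it through.** The documents give no figure for the effect of this rule, so the timing is worked out from the schedule, with weeks counted from Cycle 1 Day 1 and early termination read as End of Treatment.

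**PSA.** Cycle 3 Day 1 is Day 2 × 28 + 1 = 57. Cycle 4 Day 1, the Week-12 sample, is Day 3 × 28 + 1 = 85.
- An End of Treatment sample just after Cycle 3 Day 1 moves by 85 − 58 = 27 days, or 28 at the limit. If Cycle 3 Day 1 was done 7 days early (Day 50) and the sample was taken on Day 51, the gap is 34 days.
- The ±7-day window around Day 85 starts on Day 78. On the nominal schedule, samples from Days 58 to 77 are therefore labelled Week 12 while 27 to 8 days early, outside the protocol's own tolerance.
- A sample taken before Cycle 3 Day 1 goes to Cycle 3 Day 1, so the Week-12 result is not touched.

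**Scans.** Week 12 is Day 85 and Week 24 is Day 169.
- The 4-week waiver runs to Day 85 + 28 = 113, about Week 16. A scan then is labelled Week 24 although it is 169 − 113 = 56 days (8 weeks) early.
- With the Week-12 scan itself at −7 or +7 days, the gap is 169 − (78 + 28) = 63 or 169 − (92 + 28) = 49 days.
- The waiver is permissive. A scan done anyway on Day 86 would be 169 − 86 = 83 days early.

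**What the unobserved 8 weeks could hold.** Assume exponential progression with median m, so the chance of progressing in 8 weeks is 1 − 2^(−8/m). Protocol 1.3 and 8.9 give reference medians, for earlier agents, from about 15 weeks up to 6.6 months (6.6 × 365.25/84 = 28.7 weeks).
- m = 15: 1 − 2^(−8/15) = 0.31.
- m = 28.7: 1 − 2^(−8/28.7) = 0.18.

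On that assumption, 18% to 31% of subjects progression-free at Week 16 would progress before Week 24.

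**Count against Kaplan-Meier.** The plan's own benchmark (Protocol 8.9, SAP 1.3) is that more than 10 non-progressors of 20 puts the lower 90% limit above 30%. This reproduces: the exact lower limit for 11/20 is 34.7%. Now take assumed data for 20 subjects: 6 progress at Week 12, 3 leave at Week 16 with a non-progressing scan, 3 progress at Week 24, and 8 are seen progression-free at Week 24.
- Count without reassignment: 8/20 = 40% (lower limit 21.7%).
- Count with the three scans labelled Week 24: 11/20 = 55% (lower limit 34.7%).
- Kaplan-Meier: (14/20) × (8/11) = 50.9%, with or without the rule, because the three are censored at Week 16.

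These data are invented to show the mechanism; they are not a forecast.

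**Per dose level.** With 3 to 6 subjects (Protocol 3.2), one reclassified subject moves a rate by 1/6 = 17 to 1/3 = 33 percentage points. That is true of any single reclassification and is not an estimate of bias. The documents do not say how many subjects would be affected.

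**The case against.** A reader might infer that the rule biases the main Week-24 non-progression rate. The documents do not support this. SAP 6.1.1 and Table 6-1 censor a non-progressor at the date of the last adequate assessment, SAP 6.1.2 takes the Week-24 rate from that PFS analysis, and SAP 3.8.3 contrasts analyses needing one value per visit, "whereas a time-to-event analysis would not require 1 value per analysis window". Kaplan-Meier results stand as they are.

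A reader might also infer that the rule always flatters the drug. It does not: an early rise moved to Week 12 counts against it, and progression on an early-termination scan is genuine progression by Week 24.

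Other objections limit the scan part:
- SAP 6.1.1 defines the endpoint by progression status by Week 24, and nothing says the count is built from visit labels. SAP 6.1.2 leaves open how dropouts enter the count, and removing the reassignment alone would not settle that.
- SAP 6.2.2 summarises lesion response by category and treatment group without saying by visit.
- The rule concerns leaving the study, whereas End of Treatment is triggered by stopping GS-5829. Protocol 6.10 asks for scans to continue after a toxicity stop, and a real Week-24 scan would be preferred under SAP 3.8.3. Against this, Protocol 6.6 makes the 30-day visit the last one in phase 1b.

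Finally, the stakes are modest. SAP 1 says phase 2 did not open, the phase 1b primary endpoint is DLT incidence, and no formal testing is planned. All of this stands, but none of it removes the Week-12 PSA problem: that endpoint applies in phase 1b and is tied to a time point, with no date window to keep an early value out.

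**Conclusion.** The point holds for Week-12 PSA response: as written, the SAP allows a value up to about 28 days early (34 with visit windows) to be counted as the Week-12 outcome, in either direction. It holds conditionally for the Week-24 count and any by-visit lesion table, where a scan about 8 weeks early could be used if visit labels drive those outputs.

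The conclusion assumes that early termination means the End of Treatment visit. If so, the rule could reach many subjects, since SAP 1 states that all phase 1b subjects have discontinued study drug, although only those whose last PSA falls between Cycle 3 Day 1 and Cycle 4 Day 1 affect the Week-12 PSA result. The affected outputs are descriptive. It is nonetheless worth correcting, because the change is cheap and the groups are small.

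**What to change.** In SAP 3.8.2, define early termination relative to the protocol's End of Treatment visit, and state that the reassignment does not apply to efficacy data (PSA, scans, lesion response). Then:
- Use actual assessment dates, accepting a value only within ±7 days of the scheduled Week-12 PSA or Week-24 scan.
- Count subjects with no in-window PSA as non-responders. A subject who left on an early rise is then a non-responder for want of a Week-12 value, not because of the rise.
- In the Week-24 count, class subjects with no in-window scan and no earlier progression as not confirmed progression-free. Progression on an early-termination scan still counts as progression by Week 24.

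Other conventions for missing values are defensible; what matters is that one is stated. By-visit safety summaries may keep the reassignment. The cost is SAP wording, with no new data; the reported rates may be slightly less favourable.
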